### **Procedures**

**Pre-implementation Phase** (5 months). Recruitment will begin and we will identify a physician "champion" and an office staff member to lead implementation in each practice. Practices will choose by month 4 SEEKonline or the Traditional paper and pencil approach. To ease introduction of the SEEK model, we will address logistical issues such as for which checkups parents will complete the SEEK PQ and documentation in the EHR. SEEK Parent Handouts will be customized with information on local resources and PCPs will complete the SEEK Primary Care Provider Questionnaire (PCPQ) prior to the SEEK training.

**Implementation Phase.** In month 5, practices in cohort 1 will be randomized to one of the two SEEK training strategies (MOC or IND), stratified by practice type (pediatric or family medicine). At the end of training in month 8, PCPs will evaluate it. After the training, PCPs will be asked to participate in 3 webinars

every 4 months to discuss implementation and clinical issues. By month 8, interested practices will have SEEKonline connected to their EHR, ensuring interoperability. In month 9, the SEEK intervention will begin in cohort 1. Practice leaders, PCPs, behavioral health professionals and office staff will be asked to complete the online SEEK Adoption Survey, regardless of full participation. Parents also will begin completing surveys. Purposive subsamples from each group will be selected for 30-minute phone qualitative interviews. The process for cohort 2 will begin in month 11 and the SEEK intervention will start in month 16. Procedures are detailed under Human Subjects for addressing concerns of possible child abuse or neglect.

**Sustainment Phase.** Participants will be assessed at 12, 21 and 33 months post baseline regarding their thinking, feeling, behavior and experiences (see Table 3) to help inform understanding of SEEK's implementation and sustainment. At months 41 and 48, the observation period will end for cohorts 1 and 2. Final surveys and phone interviews will assess participants' thoughts and plans about continued use of SEEK. Following the grant period, practices that wish to continue utilizing the implementation strategies will be guided through the process of establishing real-world, not-grant funded contracting.

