**Final 12 months.** De-identified aggregate data will be obtained from practices' EHRs on all children (0-5) for the periods prior to and during SEEK implementation: rate of eligible visits where screening occurred, types of problems identified, types of actions taken, receipt of services, as well as CM-related diagnoses using ICD-10 codes. This will be facilitated by 4 of the 5 systems using EPIC as their EHR and having in-house IT. The data will be analyzed, the Final Report prepared, and presentations and papers will continue to be developed.

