**Table 3: Study Measures Related to Specific Aims**

Domain/Measure	Aims	Respondent*	Baseline** A: mo 8 B: mo 15	Training A: by mo 9 B: by mo 10	F/U 1 A: mo 20 B: mo 27	F/U 2 A: mo 29 B: mo 30	F/U 3 A: mo 41 B: mo 48
Organizational							
System Demographics	1, 2, 3	SL	●			●	
Evidence Based Practice Attitude Scale	1, 2, 3	All, except parents	●		●	●	●
Implementation Leadership Scale	1, 2, 3	All, except parents	●		●	●	●
Implementation Climate	1, 2, 3	All, except parents	●		●	●	
Implementation Process							
Stages of Implementation	2, 3	AS	●	●	●	●	●
Adoption							
SEEK Adoption Survey	2, 3	SL, PL, PCP	●				
Seek Training							
SEEK Training Evaluation	1, 2, 3	PCP		●			
Child Maltreatment							
EHR review****		IT			●		●
Implementation Outcomes							
SEEK PCP Questionnaire	1, 2, 3	PCP	●	●	●	●	●
SEEK PCP Survey	1, 2, 3	PCP		●	●	●	●
SEEK Office Staff	1, 2, 3	AS		●	●	●	●
SEEK Parent View	1, 2, 3	P		●	●	●	●
Rate of Screening	1, 2, 3	EHR	●	●	●	●	●
Receipt of Services	1, 2, 3	EHR	●	●	●	●	●
Costs							
Cost of Implementing New Strategies (COINS)	2, 3	PL, AS, PCP			●	●	●
General							
Qualitative Phone Interviews	1, 2, 3	All		●	●	●	●

\*SL = system leaders, PL = practice leaders, PCP = primary care providers, BHP = behavioral health professionals, AS=ancillary staff, P=parents, BHP=behavioral health professional, IT=information technology

\*\*A = 1st cohort of healthcare systems and practices, B = 2nd cohort of healthcare systems and practices

\*\*\*\*Brief Child Abuse Potential Inventory, \*\*\*\*EHRs will be reviewed by IT toward end of study

Proportion Scores are calculated separately for each stage. The total Proportion Score is based on the number of activities completed out of the number that could be completed – for each stage.

Finally, the SIC Stage Score marks the final stage that a site reaches. SIC scores are calculated within each of the three Implementation Phases: Pre-implementation (stages 1-3), Implementation (stages 4-7), and Sustainment (stage 8).

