**Aim 3. Examine the effectiveness of SEEK in reducing CM.** As in our previous studies, we will identify CM-related diagnoses, now via EHRs. We will review the EHR for each child (0-5) in each practice for two years prior to implementing SEEK and during implementation. The presence of CM-related ICD-10 codes will be recorded. The proportion of children with CM diagnoses before and during SEEK will be compared at each practice. Formal inference regarding the best estimate and statistical significance of pre-post differences will be based on a binary regression model with a random effect for site, similarly to Aim 1.

**Sample Size Considerations.** Our projected sample sizes (numbers of practices, professionals within each practice, and children in the practices) should provide good precision to estimate parameters and ample power to detect moderate associations. Table 4 below shows the detectable effect sizes for various comparisons, based on performing 2-sided .05-level tests and incorporate a 1.5-fold increase in variance and sample size to account for potential loss of power due to clustering of observations within practices and systems. In general, the detectable effect sizes are moderate, at plausible levels. We observed effect sizes of about 1.0 regarding Competence and Comfort in SEEK II. For Aim 2, assuming 90% of practices provide organizational information, we will estimate the rate of adoption of SEEK accurately,  $\pm$  15 percentage points.

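### Aim 3 H1 compares the proportion of children ever coded over 24 months before SEEK with the proportion over an undefined, probably 32-month, period during it, so window length alone raises the 'during' figure

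*Combined protocol and SAP*

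**What the plan says.** Data Analysis Plan, Aim 3: records are reviewed "for two years prior to implementing SEEK and during implementation", the presence of maltreatment-related ICD-10 codes is recorded, and "The proportion of children with CM diagnoses before and during SEEK will be compared at each practice". Inference is by binary regression with a random effect for site.

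Procedures gives the dates from which the second window can be worked out. "In month 9, the SEEK intervention will begin in cohort 1"; for cohort 2, "the SEEK intervention will start in month 16". Then: "At months 41 and 48, the observation period will end for cohorts 1 and 2". In Table 3 the last follow-up column reads "F/U 3 A: mo 41 B: mo 48" and the EHR row is marked there (and at F/U 1); the footnote adds "EHRs will be reviewed by IT toward end of study".

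Two other points bear on the denominator:

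- **Child set.** The final-12-months paragraph of Procedures asks for aggregate data "on all children (0-5) for the periods prior to and during SEEK implementation". The Child Maltreatment measures section instead describes children attending during the study, with a look-back of at most two years.
- **Time unit.** H1 in Specific Aims is worded as incidence, while Table 4 calls the measure prevalence. Neither carries a time unit.

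No section sets equal windows, annualises the proportion, or brings in child-time or an offset.

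**The concern.** The proportion of children with at least one code in a window grows with the length of the window, because each child is observed for longer on average. If 'during' is longer than 'before', the 'during' proportion is higher even when nothing has changed. A random site effect cannot remove this: every practice has the same imbalance, so it goes straight into the pre-post coefficient.

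The pre-post comparison is the only Aim 3 analysis the plan spells out. A real reduction could be reported as no change, or as an apparent increase in maltreatment after a prevention programme was introduced. Because Procedures and the Child Maltreatment section say the data arrive as de-identified aggregates, periods not specified in the request may not be separable afterwards.

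**Working it through.** **Windows.** Before: 24 months (Aim 3). During: 41 − 9 = 32 months in cohort 1 and 48 − 16 = 32 months in cohort 2. The 32 months is derived from Procedures; it is not stated as the EHR window.

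**The plan's yardstick.** Table 4 gives 5% vs 4.5% and 10% vs 9.6% as detectable with 98,000 per group at 80% power, two-sided 0.05. With the 1.5-fold variance inflation, solving d = (1.96 + 0.842) × √[1.5(p₁q₁ + p₂q₂)/98,000] gives detectable falls of 0.33 points from 5% and 0.46 points from 10% (to 4.67% and 9.54%). The stated pairs are therefore not exactly reproduced. That is a separate matter; they serve here only as the effect sizes the plan has in mind.

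**Model (assumptions).** Steady open panel, constant code rate h, and a fixed stay of A years per child. The documents give no stay, so A is varied. For a window of W years, entry times u are uniform on (−A, W) and observed time is t = min(u + A, W) − max(u, 0), with mean WA/(W + A). The proportion coded is the mean of 1 − exp(−ht). I set h so that 24 months gives 5% and then apply it to 32 months. For the true-effect case, h is set so that 24 months would give 4.5%, a rate ratio of 0.897.

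**Worked case, A = 2.** Mean time is 2×2/4 = 1.00 year before and 2.667×2/4.667 = 1.143 years during. The no-effect proportion rises from 5% to 5.69%. The standard error is √[1.5(0.05×0.95 + 0.0569×0.9431)/98,000] = 0.00124, so z = 0.0069/0.00124 ≈ 5.5.

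| Stay A (years) | Time ratio, 32 vs 24 mo | No effect: 5% becomes | True 5% to 4.5% shows as | z of that (N = 98,000) | Rate reduction needed to show equality |
|---|---|---|---|---|---|
| 0.5 | 1.053 | 5.26% | 4.73% | −2.2 | 5.1% |
| 1 | 1.091 | 5.45% | 4.90% | −0.8 | 8.4% |
| 1.5 | 1.120 | 5.58% | 5.03% | +0.2 | 10.8% |
| 2 | 1.143 | 5.69% | 5.12% | +1.0 | 12.5% |
| 3 | 1.176 | 5.84% | 5.26% | +2.1 | 14.9% |
| 6 | 1.231 | 6.10% | 5.50% | +4.0 | 18.7% |

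The z values follow Table 4 in treating the periods as independent groups of equal size.

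- With no effect, z runs from 3.6 (A = 1) to 8.7 (A = 6).
- The 0.5-point fall disappears entirely at A = 1.4. It becomes a significant rise from about A = 2.8 (2.9 with the 90,000 children given under Sample).
- Table 4's other pair, 10% vs 9.6%, shows as 10.4% to 11.6% for A from 1 to 6, a rise throughout.
- Exponentially distributed stays with means of 1 to 6 years give 4.88% to 5.50% for the true-effect column, so the fixed-stay assumption matters little.
- At a 1% base rate, the low end of the range in Table 4's footnote, no effect shows as 1.09% to 1.23% (z 1.6 to 3.9). A fall to 0.9% shows as 0.98% to 1.11% (z −0.3 to +1.9). The relative distortion is the same, but the falsely significant rise for a true fall does not appear.

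**The case against.** The strongest reply is that the 'during' window is undefined rather than 32 months.

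- **Phase headings.** The month 41 and 48 endpoints stand under the Sustainment Phase, while Aim 3 speaks of implementation.
- **Table 3.** The EHR row is also marked at F/U 1 (months 20 and 27). If that mark split the period, the segments would be 11 months (20 − 9 and 27 − 16) and 21 months (41 − 20 and 48 − 27), both shorter than 24. The bias would then favour SEEK: with no effect, 5% becomes 4.78% (A = 1) to 4.53% (A = 6) over 21 months.
- **Timeline.** It ends observation at months 46-48 without separating cohorts, giving cohort 1 between 37 and 39 months (46 − 9 and 48 − 9).
- **Look-back wording.** The limit of up to two years in the Child Maltreatment section might be stretched to cover both periods.

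It can also be said that the bias is conservative on the 32-month reading, that H1 is an uncontrolled secondary contrast in an implementation trial, and that the extract is still to be specified.

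Some of this stands: the direction depends on 'during' exceeding 24 months, and the size on an assumed stay. It does not rescue the plan. Aim 3, the final-12-months paragraph and the Table 3 footnote describe one late extract covering the whole SEEK period. The Timeline reading makes the imbalance worse (5.65% to 6.92% with no effect). The look-back wording also permits a 'before' window shorter than 24 months, which widens the gap. Any length other than 24 months needs the same correction. A conservative bias that can hide the planned effect, or show harm, is not a safe one.

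**Conclusion.** The concern holds. Followed as written, with the dates under Procedures, the H1 contrast is biased against SEEK. At a 5% base rate the artefact is 0.45 to 1.10 points for stays of 1 to 6 years, against the 0.5-point fall in Table 4. True rate reductions of up to 8% (1-year stay) to 19% (6-year stay) would show as no change or a rise, and larger ones would be understated.

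The direction holds at every stay length provided 'during' is longer than 'before'. The size rests on the assumed stay, a constant code rate and a steady panel. Only H1 is affected: the MOC and IND arms share the same windows, so H2 is not biased by this, and Aims 1 and 2 do not use the comparison. It should be fixed before the data request goes out.

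**What to change.** Before the EHR request in months 49-60, make these changes in the Aim 3 paragraph and in the request itself:

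1. **Equal windows.** Define 'before' and 'during' windows of the same length, for example 24 months each, or annual periods. State which months form 'during'. The first 24 months (9-33 and 16-40) include start-up; the last 24 (17-41 and 24-48) leave out the first eight months. Name one as the main analysis and the other as a sensitivity analysis.
2. **One child population.** Reconcile the Child Maltreatment section with Procedures and Aim 3, so that each period counts all children 0-5 on the panel in that period. Reconcile the end of observation between Timeline and Procedures.
3. **Rate analysis where possible.** If systems can supply child-time, analyse coded children per child-year with a log child-time offset. This uses all 32 months and matches H1's wording of incidence.

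**Cost.** Equal windows need only a definition. Eight of the 32 'during' months leave the main contrast. The children retained are (A + 2)/(A + 2.667), or 0.82 at A = 1 and 0.92 at A = 6, so 8% to 18% fewer in that period. With the 1.5-fold inflation, the detectable fall from 5% is about 0.33 to 0.35 points starting from 98,000 per period, or 0.35 to 0.36 from 90,000, both inside Table 4's 0.5. Child-time is a larger request, and the documents do not show that every system can meet it, so it comes second.

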### Studies' Findings

**Impact on PCPs.** In both studies, PCPs in SEEK practices reported significantly greater comfort and perceived competence in addressing the targeted risk factors, compared to controls. Improvements were sustained for 18-36 months. Review of medical records revealed that PCPs in SEEK practices were significantly more likely than controls to screen for the targeted risk factors for CM. In SEEK II, this was confirmed by direct observation; screening increased on average across practices from less than 5% to 62% of visits. In SEEK I, parents in SEEK clinics reported more favorable views of their child's PCP. Importantly, busy PCPs demonstrated they could effectively implement SEEK.

**Impact on CM.** Three measures from three sources assessed CM: 1) parent self-report on the Conflict Tactics Scale, 2) review of children's medical records for abuse or neglect, and 3) CPS reports. *Parent self-report.* SEEK I parents reported fewer "severe physical assaults" than controls (0.11 vs. 0.33,  $p = .04$ ). SEEK II parents reported fewer instances of Psychological Aggression ( $p = .02$ ) and Minor Physical Assaults ( $p < .05$ ) than did controls. *Medical records.* Children in SEEK I practices had less medical neglect than did controls. There was less "non-compliance" with medical care (4.6% vs. 8.4%,  $p = 0.05$ ), and fewer delayed immunizations (3.3% vs. 9.6%,  $p = 0.002$ ). *CPS reports.* In SEEK I, fewer families were reported to CPS (12% vs. 19.7%,  $p = .04$ ). A report was prevented in one of every 13 such families exposed to SEEK.

**Time Required.** SEEK did not require significantly more time, on average, for PCPs to address psychosocial problems. Parents completing the PQ before visits saved time; this was offset when addressing problems.

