nested within practices which are nested within the 5 healthcare systems. The participating systems will be randomized to one of two start times - 9 or 16 months from project start date, beginning with one pediatric and one family medicine system (cohort 1). Staggering the start time addresses the capacity limitations of the training and research staff.

**Sample.** We will offer SEEK to the 5 healthcare systems. Inclusionary criteria are: 1) practices not already implementing SEEK, 2) practices providing primary care to children, and 3) agreement to participate. The systems have indicated a general commitment to this project; they include 59 practices with 306 PCPs. Our recruitment efforts in SEEK II were very successful with 75% (18/24) of practices agreeing to participate, including all the PCPs in those practices. We plan to study 13 pediatric and 35 family medicine practices. If more practices are interested, we will select the first 48 choosing to participate. In the unlikely event that fewer than 48 are interested, we will approach other healthcare systems. In addition to 5 system leaders, we will recruit 5 groups of participants: 1) all 48 practice leaders, 2) 275 PCPs, 3) 16 behavioral health professionals, 4) 96 ancillary staff, and 5) 288 parents (6 per practice). These estimates are based on current staffing. Smaller subsamples will be purposively selected for qualitative interviews according to practice type, training strategy and presence of integrated behavioral health.

We will also request limited consent from practice leaders and PCPs who opt out to briefly probe their decision. We will ascertain aggregated ICD-10CM-related diagnoses on all children 0-5 attending the practices (N~90,000). Based on our experience, we anticipate 60% of practice leaders and PCPs will be female as will be most of the other participants. Different regions provide diversity in terms of urban, suburban and rural locations, and racial/ethnic diversity (e.g., 2 systems serve a predominantly Latino population). Three systems have integrated behavioral health professionals. These contextual factors will be considered in all analyses.

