**Table 4. Power Calculations**

Aim	Respondents/Source	Measure	N per group	Detectable Effects with 80% power
1a	PCPs	Changes in Comfort and Competence in addressing CM	137	Effect size  of 0.42
1a	Parents	Parent satisfaction	144	Effect size  of 0.41
1b	Staff	Staff Perceptions	24/72 	Effect size  of 0.82
2	Practices	Proportion adopting	59	Precision of +/- 15 pct points
3	EHR	Pre-post prevalence of CM-related diagnoses	98,000	5% vs. 4.5%  10% vs. 9.6%

Defined as the difference in means between groups divided by the standard deviation.

Conservatively assuming an imbalance between SEEKonline vs. Traditional of as much as 25% to 75%.

In our previous evaluations of SEEK, we observed rates of CM in the medical record ranging from 5% to 1%.

methods.

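### Table 4's two detectable differences for Aim 3 do not follow from the stated inputs, and no single N or inflation factor gives both

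*Combined protocol and SAP*

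**What the plan says.** The Sample Size Considerations paragraph of the Data Analysis Plan says that the effects in Table 4 are "based on performing 2-sided .05-level tests". On clustering, it adds that the calculations "incorporate a 1.5-fold increase in variance and sample size to account for potential loss of power due to clustering". Table 4 heads its last column "Detectable Effects with 80% power".

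The Aim 3 row, "Pre-post prevalence of CM-related diagnoses", has 98,000 in the per-group column and lists two detectable pairs: 5% vs 4.5% and 10% vs 9.6%. Footnote 3, attached to the first pair, says of the earlier SEEK evaluations that "we observed rates of CM in the medical record ranging from 5% to 1" per cent.

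The Sample paragraph of the design section gives a different count: "all children 0-5 attending the practices (N~90,000". The planned Aim 3 analysis is a "binary regression model with a random effect for site". For Aim 3 the documents give no intracluster correlation, no other design effect and no pre-post correlation.

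**The concern.** The Aim 3 row looks wrong before any calculation. The variance of a proportion, p(1−p), is larger at 10% than at 5%. With the same number of children, inflation, power and significance level, the smallest detectable absolute difference must therefore be larger at 10%. The table has it smaller: 0.4 points at 10% and 0.5 points at 5%.

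This is the plan's only power statement for the aim on preventing child maltreatment. If the entries do not follow from the stated inputs, a reader cannot tell which N, factor or definition of period lies behind them. The reader also cannot rely on 80% power for the 10% scenario.

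**Working it through.** **Inputs.** Two-sided 0.05 (z = 1.960) and the 1.5-fold inflation come from Sample Size Considerations. Power of 80% (z = 0.842), 98,000 per group and the two pairs come from Table 4. The alternative count of about 90,000 comes from the Sample paragraph.

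**Step 1. How the 1.5 was used elsewhere in the table.** For the standardised effects in the Aim 1 rows,

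d = (1.960 + 0.842) × √[1.5 × (1/n₁ + 1/n₂)].

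- 137 and 137: 0.415 (0.417 with the t distribution). Printed: 0.42.
- 144 and 144: 0.404 (0.406). Printed: 0.41.
- 24 and 72: 0.809 (0.82). Printed: 0.82.

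These rows approximately reproduce with 1.5 applied once.

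**Step 2. N needed for the printed Aim 3 pairs.** The pooled two-proportion formula, before inflation, is

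n = [1.960 √(2p̄(1−p̄)) + 0.842 √(p₁(1−p₁) + p₂(1−p₂))]² / (p₁ − p₂)².

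- 5% vs 4.5%: (0.5896 + 0.2532)² / 0.005² = 28,408; × 1.5 = 42,612 per group.
- 10% vs 9.6%: (0.8241 + 0.3539)² / 0.004² = 86,726; × 1.5 = 130,089 per group.

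Unpooled (28,406; 86,723), arcsine (28,390; 86,718) and continuity-corrected (28,807; 87,225) versions agree closely, so the choice of formula does not explain the mismatch. At 98,000 the implied inflation factors are 98,000/28,408 = 3.45 and 98,000/86,726 = 1.13.

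**Step 3. Allow for rounding of the second rate.** With the 1.5 factor:

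- 4.45% to 4.55% needs about 35,000 to 52,900 per group.
- 9.55% to 9.65% needs about 102,600 to 170,300 per group.

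The ranges do not overlap, and neither contains 98,000 or 90,000. The implied factors at 98,000 (2.78 to 4.20, and 0.86 to 1.43) do not overlap either, and neither range contains 1.5.

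**Step 4. What the stated inputs detect.** The effective size is 98,000/1.5 = 65,333 per group. Solving for the second rate at 80% power gives 5% vs 4.668% and 10% vs 9.540%. The differences are 0.332 and 0.460 points, a ratio of about 1.38. As a check, √[(0.10 × 0.90)/(0.05 × 0.95)] = √1.895 = 1.38.

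**Step 5. Power for the printed pairs.**

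| N per group, with 1.5 | 5% vs 4.5% | 10% vs 9.6% | 10% vs 9.55% |
|---|---|---|---|
| 98,000 | 98.9% | 68.1% | 78.2% |
| 90,000 | 98.3% | 64.4% | 74.7% |

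**Step 6. Other readings of the inputs.**

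| Reading | Second rate against 5% | Second rate against 10% | Which printed entry matches |
|---|---|---|---|
| 98,000 per group, factor 1.5 | 4.67% | 9.54% | neither |
| 98,000 per group, no inflation | 4.73% | 9.62% | 10% pair only |
| 98,000 per group, factor 1.5 × 1.5 = 2.25 | 4.59% | 9.44% | neither |
| 90,000 per group, factor 1.5 | 4.65% | 9.52% | neither |
| 98,000 in total (49,000 per period), factor 1.5 | 4.53% | 9.35% | 5% pair only |

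None of these readings gives both entries. By the ordering argument under the concern, no other common N and factor can do so.

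**The case against.** The strongest reply is that little depends on this row.

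- **No design consequence.** All children aged 0-5 in the practices are included, so the row does not set N, and no hypothesis, test or sample changes. This stands.
- **A near miss at 10%.** The detectable value is 9.540%, and 9.55% would round to the printed 9.6%. The 68.1% figure takes 9.6% as exact; at the rounding edge power is 78.2%. This also stands, but it concerns only the size of that error. It does not reconcile the two entries.
- **The 5% entry is safe.** It is conservative if 98,000 is per group and about right if it is a total. As footnote 3 reads, its range covers 5% and not 10%. However, Studies' Findings reports control rates of 8.4% for non-compliance with medical care and, for immunizations, "fewer delayed immunizations (3.3% vs. 9.6" per cent. I therefore do not argue that 10% is implausible.
- **A typing slip.** If the tenths digits were swapped (4.6% and 9.5%), both would fit 98,000 with one factor between about 1.67 and 2.15. This is conjecture, and the range excludes the stated 1.5. The row would still need correcting.
- **False precision in a recalculation.** The factor 1.5 is unsupported by any intracluster correlation. With 98,000/48 ≈ 2,042 children per practice, it implies (1.5 − 1)/2,041 ≈ 0.0002. Children may also contribute to both periods. These are fair cautions about the adequacy of 1.5, which is a separate question. They do not rescue the row: an assumed pre-post correlation of 0.2 gives 4.70% and 9.59%, which fits the 10% pair but moves further from 4.5%.

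**Conclusion.** The concern holds. Under the plan's own inputs the Aim 3 entries should read 5% vs 4.67% and 10% vs 9.54%. The printed 4.5% is conservative by 0.17 points, and the printed 9.6% is optimistic by 0.06 points. The claim of 80% power for 10% vs 9.6% is not met at 98,000 per group, where power is 68.1%, or 78.2% at best after rounding.

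The mutual inconsistency of the two entries needs only a common N, factor, power and significance level. The specific replacement values rest on two independent periods of equal size and on a single 1.5 inflation, which is how the Aim 1 rows approximately reproduce. The errors are small and do not affect the design, but the statement is wrong as printed and should be corrected.

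**What to change.** Reconcile the 98,000 in Table 4 with the roughly 90,000 in the Sample paragraph, state whether the figure is per period or a total over both periods, and restate both entries from that one N with the stated 1.5:

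- 98,000 per period: 5% vs 4.67% and 10% vs 9.54%.
- 90,000 per period: 5% vs 4.65% and 10% vs 9.52%.
- 98,000 as a total over two equal periods (49,000 each): 5% vs 4.53% and 10% vs 9.35%.

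Add a note that the row treats the two periods as independent samples with an inflation factor of 1.5. The cost is a one-row table edit, with no change to design or analysis. At 98,000 per period the claim becomes slightly less favourable at 10% and more favourable at 5%.

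### A single, unsupported 1.5-fold clustering factor covers clusters of 2 staff and of about 2,000 children, and the Aim 3 row of Table 4 does not follow from it

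*Combined protocol and SAP*

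**What the plan says.** Under Data Analysis Plan, Sample Size Considerations, the detectable effects in Table 4 are described as "based on performing 2-sided .05-level tests" and as calculations that "incorporate a 1.5-fold increase in variance and sample size to account for potential loss of power due to clustering". The text names clustering within practices and systems as the reason, and gives no ICC, cluster size or between-period correlation. It concludes that power is ample for moderate associations.

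Table 4 has a column headed "Detectable Effects with 80% power". Its Aim 3 row, "Pre-post prevalence of CM-related diagnoses", lists 98,000 per group with two detectable pairs: 5% vs 4.5% and 10% vs 9.6%.

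The Sample paragraph plans 48 practices (13 pediatric, 35 family medicine), 275 PCPs, 96 ancillary staff and "288 parents (6 per practice"). It puts the children aged 0-5 at "attending the practices (N~90,000"), not 98,000.

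For the Aim 3 analysis the plan states: "The proportion of children with CM diagnoses before and during SEEK will be compared at each practice". Inference is to be "based on a binary regression model with a random effect for site". No term lets the pre-post change differ between practices.

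**The concern.** The usual design effect is 1 + (m - 1) x ICC, where m is the number of observations per practice. One factor cannot suit m = 2 and m = 2,000 unless the ICC happens to differ about 2,000-fold between those outcomes, and the plan does not argue that it does.

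The row most exposed is Aim 3, the trial's only test of whether SEEK prevents child maltreatment. The plan itself expects the change to differ between practices: Aim 3 H2 predicts a difference between MOC and IND practices, and Aim 3 relates maltreatment rates to implementation success. If that variation is larger than the power calculation allows, a null Aim 3 result could be read as evidence of no effect when the study could not reliably see the stated difference. An analysis model that leaves the same variation out would also give intervals that are too narrow.

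**Working it through.** **1. Aim 1 rows.** A two-sample t calculation at 80% power, with each group size divided by 1.5, gives 0.417 for PCPs (137 per group; printed 0.42), 0.406 for parents (144 per group; printed 0.41) and 0.822 for staff (24/72; printed 0.82). All three reproduce, so the flat 1.5 was used there.

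**2. ICC implied by 1.5 as an ordinary design effect**, ICC = 0.5/(m - 1):
- staff, m = 96/48 = 2: 0.50
- PCPs, m = 275/48 = 5.73: 0.106
- parents, m = 6: 0.10
- children, m = 98,000/48 = 2,042: 0.000245 (90,000/48 = 1,875 gives 0.000267)

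**3. The quantity that matters for Aim 3.** The contrast is before versus during in the same practices, so stable differences between practices cancel. With J practices, m children per practice per period and SD of true practice-level change s, the variance of the mean change is [2p(1-p)/m + s²]/J. Relative to independent children the factor is

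F = 1 + m s² / [2p(1-p)].

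Setting F = 1.5 at p = 5% gives s = sqrt(0.5 x 2 x 0.05 x 0.95 / 2,042) = 0.0048, or 0.48 percentage points.

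**4. The Aim 3 row under the plan's own inputs.** Effective n = 98,000/1.5 = 65,333 per period. The detectable difference is (1.96 + 0.84) x sqrt{[p1(1-p1) + p2(1-p2)]/n}:
- from 5%: 2.80 x sqrt(0.0920/65,333) = 0.33 points, so 5% vs 4.67% (printed 4.5%)
- from 10%: 2.80 x sqrt(0.1763/65,333) = 0.46 points, so 10% vs 9.54% (printed 9.6%)

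Power for the printed pairs:
- 5% vs 4.5%: 0.005/sqrt(0.090475/65,333) = 4.25; 4.25 - 1.96 = 2.29; power 98.9%
- 10% vs 9.6%: 0.004/sqrt(0.176784/65,333) = 2.43; 2.43 - 1.96 = 0.47; power 68%

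Neither is 80%, and they miss in opposite directions.

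**5. Factor at which each printed pair has exactly 80% power.** The required n per period is about 28,400 for 5% vs 4.5% and about 86,700 for 10% vs 9.6%. Dividing 98,000 by these gives factors of 3.45 and 1.13. Converted to SD of change by step 3, these are sqrt(2.45 x 0.095/2,042) = 1.07 points and sqrt(0.13 x 0.18/2,042) = 0.34 points.

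**6. Other readings tried.** None gives 80% for both pairs:

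| Reading | Power, 5% vs 4.5% | Power, 10% vs 9.6% |
|---|---|---|
| 98,000 per period, no inflation | 99.9% | 84.6% |
| 98,000 per period, 1.5 applied twice (2.25) | 93.4% | 51.0% |
| 90,000 per period, factor 1.5 | 98.3% | 64.4% |
| 90,000 per period, no inflation | 99.9% | 81.4% |
| 98,000 as the total (49,000 per period), factor 1.5 | 85.2% | 40.5% |

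The 10% pair comes close to 80% only when no clustering allowance is made.

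**7. Sensitivity at a 5% base rate**, 98,000 per period. The SDs are assumptions, because the documents give none:

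| SD of change (points) | Factor F | Power, 5% vs 4.5% | Detectable rate at 80% power |
|---|---|---|---|
| 0.5 | 1.54 | 98.7% | 4.66% |
| 1 | 3.15 | 83% | 4.52% |
| 1.5 | 5.84 | 58% | 4.35% |
| 2 | 9.60 | 39% | 4.18% |

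The calculation takes 48 practices of equal size.

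**The case against.** The best defence has four parts.

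First, an ICC of 0.00025 for children looks absurd, and a reader might infer that the Aim 3 row assumes almost no clustering. That reads a between-practice design effect into a within-practice contrast. With between-period correlation CAC, the factor is (1 - ICC) + m x ICC x (1 - CAC). An ICC of 0.005 with CAC 0.95 gives 1.51, which is not negligible clustering. This stands, and it is why the working uses the SD of change.

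Second, a reader might infer that the design lacks the sensitivity claimed for 5% vs 4.5%. The documents do not show this. That pair is less demanding than a factor of 1.5 would allow, and it survives an SD of change of 1 point. It fails only at larger SDs, for which the documents give no more support than for 0.48. This stands too: for that pair, the loss of power is conditional.

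Third, the plan claims ample power only for moderate associations. Even at an SD of 2 points the detectable drop from 5% to 4.18% is a 16% relative reduction. The SEEK I record-based contrasts reported under Impact on CM (4.6% vs 8.4%, 3.3% vs 9.6%) are reductions of 45% and 66%, though in a higher-risk sample and a different comparison. This limits the practical damage but does not repair the printed figures.

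Fourth, the staff row is conservative. An ICC of 0.05 to 0.20 would give about 0.68 to 0.73 instead of 0.82, and an overcautious figure misleads nobody. Agreed; restating it is optional.

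None of this rescues 10% vs 9.6%, which fails under the plan's own factor with no outside assumption.

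**Conclusion.** The point holds in three parts.

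- The 1.5 is one unexplained number applied across cluster sizes that differ about 1,000-fold. It fits PCPs and parents (implied ICC about 0.10) but has no stated basis for the children.
- The Aim 3 row is wrong as printed, whatever one believes about clustering. Its two pairs imply incompatible factors, 3.45 and 1.13, and neither is 1.5. The 10% vs 9.6% figure is over-claimed, at 68% power rather than 80%.
- Whether 5% vs 4.5% is over-claimed depends on an input that the plan omits. It is sound if the SD of practice-level change is at most about 1.07 points. Power falls to 58% at 1.5 points and 39% at 2 points.

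The first two parts rest only on figures in the documents and the standard two-proportion calculation. The third rests on assumed SDs and equal practice sizes. The stronger conclusion, that the trial cannot detect what it says for Aim 3, is not supported for the 5% pair.

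**What to change.** In Table 4 and Sample Size Considerations:

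1. Recalculate the Aim 3 row with F = 1 + m x (variance of practice-level change)/[2p(1-p)], stating m and the assumed SD. Show detectable differences for SDs of 0.5, 1, 1.5 and 2 points.
2. Correct or remove 10% vs 9.6%. Footnote 3, as it reads, gives observed rates of 5% to 1%, so 10% lies outside the range that it cites.
3. Reconcile 98,000 with the roughly 90,000 in the Sample paragraph, and say whether the figure is per period.
4. Limit the claim of ample power for Aim 3 to the range that the recalculation supports.

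In the Aim 3 analysis, add a practice-by-period random effect so that the model carries the same variation as the power calculation.

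Before the during-SEEK data are compared, check the assumed SD against year 1 versus year 2 of the pre-SEEK records already being extracted, split by practice and year. Sampling error must be subtracted: at 5% and 2,042 children per practice per year it alone gives an SD of change of sqrt(0.095/2,042) = 0.68 points. The check captures ordinary drift and not variation in response to SEEK, so it is more likely to understate the SD than to overstate it.

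The cost is a recalculated table, one more model term, a less favourable stated sensitivity and slightly wider intervals. No additional practices or data sources are needed.
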